7.3 Per-Protocol Set

The per-protocol (PP) set is a subset of the FAS, which will include those subjects (and their visits) who do not have a protocol deviation likely to seriously affect the primary outcome of the study as judged by a masked evaluation prior to the unmasking of the study treatment, including non-compliance of study drug. Additionally, masked evaluators will determine if the data associated with the deviation will be excluded from the PP population. This population will be the secondary population for efficacy analyses and will be used to summarize a subset of efficacy variables. If the PP and FAS populations are exactly the same, then additional efficacy analyses on the PP population will not be performed. The PP population will summarize subjects as treated.

7.4 Safety Set

The safety set will include all randomized subjects who have received at least one dose of study medication. This population will be used to summarize safety variables and will summarize subjects as treated.

8. General Statistical Considerations

8.1 Unit of Analysis

Safety endpoints will be analyzed for both eyes. For subject-level efficacy endpoints, the unit of analysis will be the subject. For efficacy endpoints assessed on each eye individually, the unit of analysis will be the

analysis eye. The analysis eye is defined as the eye that met all of the inclusion criteria. If both eyes met all of the inclusion criteria, then the analysis eye will be the eye with the highest *Demodex* density at the Screening visit or, if both eyes have equal *Demodex* density, the right eye.

8.2 Missing or Inconclusive Data Handling

The primary efficacy analysis will be conducted with missing data and intercurrent events handled in the following manner:

- Discontinuation of study medication and non-optimal compliance is ignored [treatment policy strategy].
- Withdrawal due to lack of efficacy or AEs: missing data will be imputed as failure [hypothetical strategy].
- Missing data without withdrawal or withdrawal due to reasons other than lack of efficacy or AEs: missing data will be imputed employing Multiple Imputation (MI) using randomized treatment-based Markov Chain Monte Carlo (MCMC) methodology [hypothetical strategy].

In the event that the percentage of missing data due to discontinuation of study medication and non-optimal compliance exceeds 2%, these missing data will be imputed as failures and the primary efficacy analysis repeated in a separate analysis.

Sensitivity analyses on the primary efficacy endpoint are described in the Efficacy Analysis section.

Partial/missing start and end dates for AEs and concomitant medications will be imputed as follows:

Partial/missing start date:

- Dates with missing day only will be imputed as the 1st of the month unless the month and year are same as the month and year of first dose of study medication, in which case missing day will be imputed as the first dose day of study medication.
- Dates with both day and month missing will be imputed as 1 Jan unless the year is same as the year of first dose of study medication, in which case missing day and month will be imputed as the first dose day and month of study medication.
- Completely missing dates will be imputed as the first dose date of study medication unless the end date is on or before the first dose date of study medication, in which case missing date will be imputed as 1 Jan of the same year as the end date.

Partial/missing end date:

- Dates with missing day only will be imputed as the last day of the month unless the month and year are the same as the month and year of the last dose of study medication, in which case missing day will be imputed as the last dose day of study medication.

- Dates with both day and month missing will be imputed as 31 Dec unless the year is same as the year of the last dose of study medication, in which case missing day and month will be imputed as the last dose day and month of study medication.
- If the ongoing flag is missing or “Yes” then the date will not be imputed unless death date is available, in which case the missing date will be imputed as the death date. If ongoing is “No” then the missing end date will be imputed as the last dose date.
- If the imputed date is after the date of death, then the end date will be set equal to the date of death.

The original dates will be displayed in data listings and the imputed dates will be used in derivations only (study day, treatment-emergence status, etc).

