7.1 Full Analysis Set

The full analysis set (FAS) will include all randomized subjects. This population will be the primary population for efficacy analyses, and will be used to summarize all efficacy variables and will summarize subjects as randomized.

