7.2 COVID-19 Analysis Set

The Coronavirus Disease 2019 (COVID-19) pandemic is continuing during the treatment phase of this study and has impacted the conduct of this clinical study. Challenges from quarantines and potential site closures may lead to difficulties in meeting protocol-specified procedures. Protocol deviations related to COVID-19 will be documented at the subject level. Prior to unmasking, COVID-19-related protocol deviations will be assessed for their significance based on their impact to primary endpoint data.

The COVID-19 analysis set includes all randomized subjects, but excludes subjects that discontinued due to COVID-19 complications, subjects that would have discontinued due to COVID-19 had they remained on study, and subjects that had significant COVID-19-related protocol deviations. Subjects that would have discontinued due to COVID-19 had they remained on study will be determined and documented prior to unmasking. Protocol deviations will be assessed prior to unmasking for their significance based on their impact to primary endpoint data. Sensitivity analyses of the primary efficacy and key secondary analyses will be performed on the COVID-19 population and subjects will be analyzed as randomized if at least 5% of subjects met this criteria.

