8.5 Adjustments for Multiplicity

A closed hierarchical testing structure will be used where the analysis will be performed for the primary efficacy endpoint, and, only if successful, the analysis will be performed for the two secondary efficacy

endpoints using the Hochberg testing strategy. Specifically, if the null hypothesis, H_{01} , is rejected at a one-sided α of 0.025, the study will be considered a success for clinical cure and the two secondary efficacy endpoints will be tested using the Hochberg testing strategy with an α of 0.025. If the null hypothesis, H_{01} is not rejected at a one-sided α of 0.025, testing will stop and the two secondary efficacy hypotheses will be deemed not statistically significant.

9. Disposition of Subjects

Subject disposition will be presented in terms of the numbers and percentages of subjects who were randomized to masked study medication with subcategories of dosed with the masked study medication, did not dose with masked study medication; who were included in the following analysis populations: FAS, PP set, safety set; and who completed the study and discontinued from the study. Subjects who are not discontinued from the study will be considered study completers. Disposition will be summarized by treatment group and for all subjects. Subject enrollment and disposition will be summarized by treatment group and site. Percentages will be calculated using randomized subjects as the denominator unless otherwise specified.

The reasons for premature study discontinuation will be summarized by treatment group for all discontinued subjects. Percentages will be calculated using randomized subjects as the denominator. The reasons for study discontinuation that will be summarized include: AE, significant study treatment non-compliance per PI determination, pregnancy, exclusion criteria, reasons relating to COVID-19, and other. A subject listing will be provided that includes the date of and reason for premature study discontinuation.

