13.1 Primary Analysis

The primary efficacy endpoint is cure based on collarette score of 0 for the upper eyelid of the analysis eye at Day 43. The primary efficacy endpoint will be conducted on the FAS, with intercurrent events handled as described in Section 8.2. Descriptive statistics will be presented by treatment arm. Testing of the percentage of subjects cured at Day 43 based on the collarette grade will be completed using a difference of proportions test.

As specified in Section 8.2, missing data without withdrawal or withdrawal due to reasons other than lack of efficacy or AEs will be imputed employing MI using randomized treatment-based MCMC methodology.

The following SAS code will be used to generate the multiple imputation datasets:

```
PROC MI DATA=INDATA SEED=56636 NIMPUTE=20 OUT=OUT1 MINIMUM=0 MAXIMUM=4 ROUND=1;
  BY TRT;
  MCMC INITIAL=EM;
  VAR BASE DAY08 DAY15 DAY22 DAY43;
RUN;
```

The multiple imputation datasets will be used to calculate cure based on a collarette score of 0 at Day 43. The following SAS code will then be used to calculate the difference of proportions for each imputed dataset and combine the analyses across imputations:

```
PROC SORT DATA=OUT1; BY _IMPUTATION_; RUN;
PROC FREQ DATA=OUT1;
  BY _IMPUTATION_ ;
  TABLES TRT*CURE / RISKDIFF CL;
  ODS OUTPUT RISKDIFFCOL2=PROP;
RUN;
PROC MIANALYZE DATA=PROP;
  WHERE ROW='Difference';
  MODELEFFECTS RISK;
  STDERR ASE;
  ODS OUTPUT PARAMETERESTIMATES=PEST;
RUN;
```

Statistical comparison between treatment groups will be one-sided using an α of 0.025.

In addition to the primary analysis, supplementary analyses are proposed under different assumptions for the estimand to assess efficacy in patients who have missing data.

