14.2 Adverse Events

An Adverse Event (AE) is defined as any untoward medical occurrence associated with the use of a drug in humans, whether or not the event is considered drug-related. All AEs will be coded using the MedDRA version 23.0.

Treatment-emergent adverse events (TEAE) are defined as any event that occurs or worsens on or after the day that randomized study treatment is initiated. It is not anticipated that any AEs will occur before treatment. However if in the unlikely event an AE recorded in the eCRF which began prior to treatment will not be included in the summary tables but will be included in the AE data listings.

Severity of an AE is defined as a qualitative assessment of the degree of intensity of an AE as determined by the Investigator or reported to him/her by the subject. The assessment of severity is made irrespective of relationship to study drug or seriousness of the event and should be evaluated according to the following scale:

- **Mild** - Events require minimal or no treatment and do not interfere with the subject's daily activities.
- **Moderate** - Events result in a low level of inconvenience or concern with the therapeutic measures. Moderate events may cause some interference with functioning.
- **Severe** - Events interrupt a subject's usual daily activity and may require systemic drug therapy or other treatment. Severe events are usually potentially life-threatening or incapacitating.

The relationship of each AE to the study drug should be determined by the Investigator using these explanations:

- **Definitely Related** – Evidence indicates a reasonable temporal sequence of the event with the study drug administration exists or that the association of the event with study drug administration is unknown and the event is not reasonably supported by other conditions such that:
 - There is a clinically plausible time sequence between onset of the AE and study treatment administration; and/or
 - There is a biologically plausible mechanism for study treatment causing or contributing to the AE; and
 - The AE cannot be reasonably attributed to concurrent/underlying illness, other drugs or procedures.

- **Potentially Related** – Evidence indicates a possible relationship to the study drug such that:

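### Does Section 8.2 leave a withdrawal for COVID-19 illness under two conflicting imputation rules?

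*SAP*

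**What the plan says.** Section 8.2 of the SAP gives two rules for missing primary data after withdrawal. The first is "Withdrawal due to lack of efficacy or AEs: missing data will be imputed as failure [hypothetical strategy". The second covers everything else: "Missing data without withdrawal or withdrawal due to reasons other than lack of efficacy or AEs: missing data will be imputed", by MI within the randomized arm. Stopping study medication while remaining in follow-up is ignored, so the split matters only when the Day 43 score is missing.

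Three other sections bear on a subject who leaves because of COVID-19 illness:

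- Section 14.2 defines an AE as "any untoward medical occurrence associated with the use of a drug in humans, whether or not the event is considered drug-related".
- Section 9 names the discontinuation reasons to be summarized: "AE, significant study treatment non-compliance per PI determination, pregnancy, exclusion criteria, reasons relating to COVID-19, and other".
- Section 7.2 defines a COVID-19 analysis set that "excludes subjects that discontinued due to COVID-19 complications". It is a sensitivity population, analysed only if at least 5% of subjects qualify.

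Section 7.1 keeps these subjects in the primary analysis: "The full analysis set (FAS) will include all randomized subjects". Sections 13.2.1 and 13.2.2 apply the Section 8.2 rules to both secondary endpoints.

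**The concern.** The two rules in Section 8.2 are meant to be exclusive, but a withdrawal for COVID-19 illness seems to fit both. By the Section 14.2 definition the illness is an AE whatever its cause, so the subject is a failure. By the Section 9 list the reason is COVID-19 and not AE, so the subject is multiply imputed. Section 8.2 does not mention COVID-19 and states no precedence. The code in Section 13.1 carries no withdrawal-reason variable.

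Two competent programmers could therefore derive different primary estimates from the same data. If the illness is about equally common in both arms, the MI reading gives the larger difference. The event is also foreseeable: Section 5 justifies the large enrolment partly by COVID-19, and Section 7.2 expects such discontinuations. A related gap is that Section 8.2 relies on withdrawals for lack of efficacy, which Section 9 does not name.

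**Working it through.** **Inputs.** From SAP Section 5: cure rates 80.0% (TP-03) and 15.8% (vehicle); 150 per arm for the power calculation; 209 per arm (418 in total) randomized; one-sided alpha 0.025. The share *c* of an arm that withdraws for COVID-19 illness with Day 43 missing is not in the documents. I assume 1–5% and also show an extreme.

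**The plan's own figure.** Planned difference: 0.800 − 0.158 = 0.642. With 150 per arm:

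- pooled rate 0.479; null SE = √(2 × 0.479 × 0.521 / 150) = 0.0577
- unpooled SE = √((0.80 × 0.20 + 0.158 × 0.842) / 150) = 0.0442
- z = (0.642 − 1.96 × 0.0577) / 0.0442 ≈ 12.0, so power exceeds 99.9%

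This agrees with the stated figure of approximately 99%.

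**The two readings, equal shares.** If MI recovers the arm's own rate, the MI reading leaves the difference at 0.642. Failure imputation multiplies each arm's rate by (1 − *c*), so the gap is 0.642 × *c*. The SE at 209 per arm is √(0.2930 / 209) = 0.0374.

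| *c* per arm | Subjects per arm (209*c*) | Difference, failure reading | Gap (points) | Gap / SE, 209 per arm | Gap / SE, 150 per arm |
|---|---|---|---|---|---|
| 1% | 2.1 | 63.6 | 0.64 | 0.17 | 0.15 |
| 2% | 4.2 | 62.9 | 1.28 | 0.34 | 0.29 |
| 5% | 10.5 | 61.0 | 3.21 | 0.86 | 0.73 |

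**Unequal shares.** The gap (MI minus failure) is 0.80 × *c*(TP-03) − 0.158 × *c*(vehicle). With 5% on TP-03 only: 0.05 × 0.80 = +4.0 points. With 5% on vehicle only: −0.05 × 0.158 = −0.8 points.

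**Extreme.** If the whole 30% discontinuation allowance were COVID-19 illness, the failure reading gives 0.70 × 0.642 = 44.9 points. Power with 209 per arm is still above 99.9%. Section 5 ties the allowance partly to sites being unable to complete the study. Withdrawals of that kind are not AEs and go to MI without ambiguity.

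**Secondary endpoints.** At 5% per arm the gap is (0.733 − 0.211) × 0.05 = 2.6 points for mite eradication and (0.733 − 0.105) × 0.05 = 3.1 points for the composite.

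**Which reading the text favours.** Section 8.2 classifies the reason for withdrawal, not the events a subject had. Section 9 is the only visible place where such reasons are set out. It keeps COVID-19 apart from AE and plans a listing of the date and reason for each discontinuation. Section 14.2 decides what is tabulated as a safety event; it does not assign withdrawal reasons. Read this way, a withdrawal recorded as COVID-19-related goes to MI. If a site recorded AE instead, the subject would be a failure. Either way, one recorded reason gives one answer. Sections 4.2, 6.1 and 8.4 have study personnel masked and the database locked before treatment codes are released.

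**The code.** Section 13.1 refers to Section 8.2 for intercurrent events and offers its code for generating and combining the imputations. After that, "The multiple imputation datasets will be used to calculate cure based on a collarette score of 0 at Day 43". Setting the failures is an ordinary derivation step in the analysis dataset, so its absence from the code does not contradict the rule.

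**The case for a change.** The strongest reply is that Section 8.2 never says the recorded disposition reason governs. Section 14.2 also plans a table of treatment-emergent AEs leading to premature discontinuation, so the SAP has a second route to an AE withdrawal, through the AE record. A COVID-19 illness could qualify by that route and not by the other. Section 7.2 requires masked decisions on deviations and on membership of the COVID-19 set, but nothing asks for a masked assignment to failure or MI. Sensitivity analyses II (all missing data by MI) and V (all missing data as failure) do not say which reading is primary, and they need not bracket the two if withdrawals differ between arms. For the secondary endpoints only the all-failure sensitivity analysis is visible.

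Much of this stands. The overlap exists, no sentence sets precedence, and at an assumed 5% per arm the gap is not trivial beside the standard error. It still falls short of a defect. The safety table counts events and is not tied to imputation. At about 21 of 418 subjects (0.05 × 418 = 20.9) the 5% trigger in Section 7.2 is also reached, so the COVID-19 set analysis would run. Below that share, with equal arms, the gap is under 3.2 points.

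The lack-of-efficacy point is weaker. Section 9 says its summarized reasons include the ones named, and the list ends with a residual category, so it is not stated to be exhaustive. The eCRF is not in the documents, so nothing can be said about how such withdrawals are recorded.

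**Conclusion.** The concern describes a missing cross-reference, not an analysis that is wrong. Analysts who take the recorded discontinuation reason as the sorting variable, which is the natural reading of Section 8.2 alongside Section 9, get one answer per subject, and MI for withdrawals recorded as COVID-19-related. Failure imputation for illness withdrawals would also be defensible. Statisticians could reasonably differ on it, so specifying MI would not be a demonstrable improvement.

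The size is 0.6–1.3 points on a planned difference of 64.2 at an assumed 1–2% per arm, and 3.2 points at an assumed 5%. With 5% in one arm only, it runs from −0.8 to +4.0 points. Superiority at the planning rates is unaffected throughout. For the primary endpoint, Sensitivity II and V show the reader both ends when withdrawals are similar across arms.

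These figures assume that Day 43 is missing for the affected subjects, that MI recovers the arm's planned cure rate, and that the planning rates hold. The illness rate itself is an assumption. No change to the plan follows.

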13.1.1.2 SENSITIVITY ANALYSIS II

The hypothetical strategy will be used for the intercurrent event. All missing data will be imputed assuming missing at random (imputing from the same treatment arm as the subject with missing data) using similar code as provided in Section 13.1 for the primary efficacy analysis.

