13.1.1.5 SENSITIVITY ANALYSIS V

The hypothetical strategy will be used for the intercurrent event. All missing data will be imputed as failure. Treatment comparisons will also be made using the difference of proportion test and Pearson's chi-squared test or Fisher's exact test if any of the expected cell counts are less than five as an additional sensitivity analysis.

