13.2 Secondary Analyses

The secondary efficacy endpoints proportion of subjects with *Demodex* eradication at Day 43 and proportion of subjects composite cure based on collarette and erythema scores at Day 43 and will be conducted on the FAS.

As specified in Section 8.2, missing data without withdrawal or withdrawal due to reasons other than lack of efficacy or AEs will be imputed employing MI using randomized treatment-based MCMC methodology. The following SAS code will be used to generate the multiple imputation datasets:

```
PROC MI DATA=INDATA SEED=56636 NIMPUTE=20 OUT=OUT1 MINIMUM=0 MAXIMUM=4 ROUND=1;
  BY TRT;
  MCMC INITIAL=EM;
  VAR BASE DAY08 DAY15 DAY22 DAY43;
RUN;
```

The multiple imputation datasets will be used to calculate cure based on each respective secondary endpoint. The following SAS code will then be used to calculate the difference of proportions for each imputed dataset and combine the analyses across imputations:

```
PROC SORT DATA=OUT1; BY _IMPUTATION_; RUN;
PROC FREQ DATA=OUT1;
  BY _IMPUTATION_ ;
  TABLES TRT*CURE / RISKDIFF CL;
  ODS OUTPUT RISKDIFFCOL2=PROP;
RUN;
PROC MIANALYZE DATA=PROP;
  WHERE ROW='Difference';
  MODELEFFECTS RISK;
  STDERR ASE;
  ODS OUTPUT PARAMETERESTIMATES=PEST;
RUN;
```

Comparisons will be one-sided using an α of 0.025.

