13.2.1 FIRST SECONDARY EFFICACY ENDPOINT

The first secondary efficacy endpoint is cure based on proportion of subjects with *Demodex* eradication of the analysis eye at Day 43, with intercurrent events handled as described in Section 8.2. Descriptive statistics will be presented by treatment arm. Testing of the percentage of subjects cured at Day 43 based on the *Demodex* eradication will be completed using a difference of proportions test. In addition, a sensitivity analysis will be conducted in which all missing data will be imputed as failure. The difference of proportion test and Pearson's chi-squared (or Fisher's exact test if any of the expected cell counts are less than five) will be used in this sensitivity analysis.

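### Does the printed SAS code drop the rule that scores lack-of-efficacy and AE withdrawals as failures?

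*SAP*

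**What the plan says.** SAP Section 8.2 handles the primary analysis in three parts. Stopping study medication and poor compliance are ignored. For the second group the rule is "Withdrawal due to lack of efficacy or AEs: missing data will be imputed as failure [hypothetical strategy". The remaining missing data are multiply imputed within randomized arm.

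Section 13.1 takes this over: "The primary efficacy endpoint will be conducted on the FAS, with intercurrent events handled as described in Section 8.2". Just before the code it limits imputation to the third group: "missing data without withdrawal or withdrawal due to reasons other than lack of efficacy or AEs will be imputed employing MI". The printed PROC MI step runs by treatment on the baseline, Day 8, 15, 22 and 43 values in INDATA. A sentence between the two code blocks then covers the endpoint: "The multiple imputation datasets will be used to calculate cure based on a collarette score of 0 at Day 43". PROC FREQ tabulates TRT*CURE and PROC MIANALYZE pools the results.

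Section 13.2 repeats the code and says: "The multiple imputation datasets will be used to calculate cure based on each respective secondary endpoint". Sections 13.2.1 and 13.2.2 each add "with intercurrent events handled as described in Section 8.2".

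Sensitivity Analysis II imputes all missing data from the subject's own arm, "using similar code as provided in Section 13.1 for the primary efficacy analysis". Sensitivity Analysis V reads: "The hypothetical strategy will be used for the intercurrent event. All missing data will be imputed as failure".

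Section 9 tabulates AE, non-compliance, pregnancy, exclusion criteria, COVID-19 and other as reasons for discontinuation. It also plans a subject listing with each reason.

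**The concern.** The failure rule is what separates the primary analysis from Sensitivity Analysis II, yet no printed line uses the withdrawal reason. PROC MI fills every missing value it finds in INDATA, including those of subjects who left for an AE or lack of efficacy. If cure were then read from the imputed Day 43 grade alone, those subjects could count as cured. Sensitivity Analysis II would be reported under the primary label, usually with a somewhat larger treatment difference.

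Two features make this look worse. The bracketed label does not separate the rules, because the SAP calls both failure scoring and own-arm imputation a hypothetical strategy. And lack of efficacy, which triggers failure scoring, is missing from the Section 9 list, so such exits might sit under other and escape the rule.

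**Working it through.** **Text against code.**

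1. The rule is stated in Section 8.2 and adopted by cross-reference in Sections 13.1, 13.2.1 and 13.2.2. Sections 13.1 and 13.2 also restrict imputation to the other missing data. Nothing in the code contradicts this.
2. The printed code does not run to a result. PROC FREQ uses CURE, but no line creates it, not even from a Day 43 grade of 0. The preparation of INDATA is not printed either. The whole derivation is left to the text, not only the failure rule.
3. Section 13.2 reuses the collarette block unchanged, with one CURE variable for two endpoints and with a Day 8 value, although SAP Table 2 schedules no mite count at Day 8. That is a separate matter. Here it shows only that the block must be adapted and cannot be the complete program.
4. Sensitivity Analysis II calls for similar code, not the same code, which fits one differing step.
5. The Section 9 list specifies a summary table and is not the collection form. AE exits can be identified from it. Lack-of-efficacy exits may be identifiable from the planned listing or the eCRF, which is not among the documents.

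**Size if the rule were omitted.** Inputs from SAP Section 5: cure 0.80 on TP-03 and 0.158 on vehicle, 150 completers and 209 randomized per arm, one-sided 0.025.

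The plan's own power first, with 150 per arm:
- mean rate (0.80 + 0.158)/2 = 0.479
- null SE = √(2 × 0.479 × 0.521/150) = 0.0577
- alternative SE = √((0.80 × 0.20 + 0.158 × 0.842)/150) = 0.0442
- (0.642 − 1.96 × 0.0577)/0.0442 = 12.0, so power exceeds 99.9%, consistent with the stated approximate 99%.

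Let f_T and f_V be the shares of randomized subjects who leave for an AE or lack of efficacy with no Day 43 grade. These shares are assumptions. If such subjects were imputed at their arm's rate, omitting the rule would shift the difference by 0.80 f_T − 0.158 f_V:

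| f_T | f_V | Without rule | With rule | Shift (points) |
|---|---|---|---|---|
| 2% | 2% | 64.2 | 62.9 | 1.3 |
| 5% | 5% | 64.2 | 61.0 | 3.2 |
| 10% | 10% | 64.2 | 57.8 | 6.4 |
| 15% | 5% | 64.2 | 53.0 | 11.2 |
| 0% | 10% | 64.2 | 65.8 | −1.6 |
| 30% | 0% | 64.2 | 40.2 | 24.0 |

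The last row puts the plan's entire 30% discontinuation into this category on TP-03 alone. The rates are then 0.56 and 0.158. With 209 per arm the null SE is √(2 × 0.359 × 0.641/209) = 0.0469 and the alternative SE is √((0.56 × 0.44 + 0.158 × 0.842)/209) = 0.0426. Then (0.402 − 1.96 × 0.0469)/0.0426 = 7.3, and power is still above 99.9%. This leaves out imputation variance.

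The formula is an approximation, not a bound. At 2% and 8.4% it gives 0.80 × 0.02 − 0.158 × 0.084 = 0.3 points; if the vehicle exits were never imputed as cured, the shift would be 0.80 × 0.02 = 1.6 points.

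A simulation used 209 per arm, 20 imputations, 15% or 30% total missing, and assumed grade distributions and exit patterns. It gave shifts of 0.5 to 0.9 points at 2%/2%, 1.3 to 2.1 at 5%/5%, and −0.1 to 0.1 when all flagged exits were for lack of efficacy at 2%/8.4%. The smallest z in any simulated trial was 8.1, against 1.96.

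**The case for a change.** The best case for a change is that the SAP says its code will be used, so the code is a commitment and the decisive step should be in it. Position matters too. The SAP gives no grade for a failure: a failing grade entered before PROC MI would feed the imputation of other subjects, whereas setting CURE to 0 afterwards would not. In the simulation, setting CURE to 0 afterwards and leaving these subjects out of the imputation differed by less than 0.1 point, but entering a failing grade beforehand was not simulated. For the secondary endpoints the plan has an all-failure sensitivity analysis but no counterpart to Sensitivity Analysis II. And Sensitivity Analyses II and V need not enclose the primary estimate: the row with vehicle exits only gives 65.8, above the 64.2 without the rule.

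What stands is that the derivation of CURE and its place relative to PROC MI are not printed, and that Section 9 could name lack of efficacy. That is missing detail, not a conflict. A code commitment that omits its outcome variable has to be completed from the text, and the text gives the rule. The strategy label does not alter the instruction, which in each place is plainly failure or imputation. If the rule were skipped for the primary endpoint, the primary result and Sensitivity Analysis II would be almost identical despite a visible count of AE withdrawals, so the slip would probably be noticed wherever it had any weight.

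**Conclusion.** The concern does not call for a change. The failure rule is stated, adopted by reference for all three tested endpoints, and not contradicted by the code, which is an excerpt without the cure derivation. An analyst who follows the text will score these withdrawals as failures.

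The size of the risk cannot be taken from the documents, which give no withdrawal shares by reason; the 30% discontinuation allowance is explained by COVID-19 and possible loss of sites. With assumed shares of 2% to 5% in each arm, omitting the rule would move the difference by about 0.5 to 3.2 points across both methods. Larger or unequal shares would move it more, from −1.6 to 11.2 points for shares up to 15% on TP-03 and 5% on vehicle or 10% on vehicle alone. Only the reported estimate is exposed. Under the planned response rates the superiority conclusion holds in every case examined. Printing the CURE step and adding a row to the Section 9 table would be tidy, but the planned analysis would be the same.
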